14.1.4 Data handling and programming rules

The following section should be used as guidance for development of the protocol, data handling procedures or programming requirements (e.g. on incomplete dates).

14.1.4.1 Study/project specific decisions

For each study (or project) various issues need to be addressed and specified in the protocol or RAP documentation. Any deviations from protocol must be discussed and defined at the latest in the RAP documentation.

The proposed primary analysis and potential sensitivity analyses should be discussed and agreed with the health authorities and documented in the protocol (or at the latest in the RAP documentation before database lock).

14.1.4.2 End of treatment phase completion

Patients **may** voluntarily withdraw from the study treatment or may be taken off the study treatment at the discretion of the investigator at any time. For patients who are lost to follow-up, the investigator or designee should show "due diligence" by documenting in the source

documents steps taken to contact the patient, e.g., dates of telephone calls, registered letters, etc.

The end of treatment visit and its associated assessments should occur within 7 days of the last study treatment.

Patients may discontinue study treatment for any of the following reasons:

- Adverse event(s)
- Lost to follow-up
- Physician decision
- Pregnancy
- Protocol deviation
- Technical problems
- Subject/guardian decision
- Death
- Progressive disease
- Study terminated by the sponsor
- Non-compliant with study treatment
- No longer requires treatment
- Treatment duration completed as per protocol (optional, to be used if only a fixed number of cycles is given)

14.1.4.3 End of post-treatment follow-up (study phase completion)

End of post-treatment follow-up visit will be completed after discontinuation of study treatment and post-treatment evaluations but prior to collecting survival follow-up.

Patients may provide study phase completion information for one of the following reasons:

- Adverse event
- Lost to follow-up
- Physician decision
- Pregnancy
- Protocol deviation
- Technical problems
- Subject/guardian decision
- Death
- New therapy for study indication
- Progressive disease
- Study terminated by the sponsor

14.1.4.4 Medical validation of programmed overall lesion response

As RECIST is very strict regarding measurement methods (i.e. any assessment with more or less sensitive method than the one used to assess the lesion at baseline is considered UNK) and not available evaluations (i.e. if any target or non-target lesion was not evaluated the whole overall lesion response is UNK unless remaining lesions qualified for PD), these UNK assessments may be re-evaluated by clinicians at Novartis or external experts. In addition, data review reports will be available to identify assessments for which the investigators' or central reader's opinion does not match the programmed calculated response based on RECIST criteria. This may be queried for clarification. However, the investigator or central reader's response assessment will never be overruled.

If Novartis elect to invalidate an overall lesion response as evaluated by the investigator or central reader upon internal or external review of the data, the calculated overall lesion response at that specific assessment is to be kept in a dataset. This must be clearly documented in the RAP documentation and agreed before database lock. This dataset should be created and stored as part of the 'raw' data.

Any discontinuation due to 'Disease progression' without documentation of progression by RECIST criteria should be carefully reviewed. Only patients with documented deterioration of symptoms indicative of progression of disease should have this reason for discontinuation of treatment or study evaluation.

14.1.4.5 Programming rules

The following should be used for programming of efficacy results:

14.1.4.5.1 Calculation of 'time to event' variables

Time to event = end date - start date + 1 (in days)

When no post-baseline tumor assessments are available, the date of randomization/start of treatment will be used as end date (duration = 1 day) when time is to be censored at last tumor assessment, i.e. time to event variables can never be negative.

14.1.4.5.2 Incomplete assessment dates

All investigation dates (e.g. X-ray, CT scan) must be completed with day, month and year.

If one or more investigation dates are incomplete but other investigation dates are available, this/these incomplete date(s) are not considered for calculation of the assessment date (and assessment date is calculated as outlined in [Section 14.1.3.2.7](#)). If all measurement dates have no day recorded, the 1st of the month is used.

If the month is not completed, for any of the investigations, the respective assessment will be considered to be at the date which is exactly between previous and following assessment. If a previous and following assessment is not available, this assessment will not be used for any calculation.

14.1.4.5.3 Incomplete dates for last known date patient alive or death

All dates must be completed with day, month and year. If the day is missing, the 15th of the month will be used for incomplete death dates or dates of last contact.

14.1.4.5.4 Non-target lesion response

If no non-target lesions are identified at baseline (and therefore not followed throughout the study), the non-target lesion response at each assessment will be considered 'not applicable (NA)'.

14.1.4.5.5 Study/project specific programming

The standard analysis programs need to be adapted for each study/project.

14.1.4.5.6 Censoring reason

In order to summarize the various reasons for censoring, the following categories will be calculated for each time to event variable based on the treatment completion page, the study evaluation completion page and the survival page.

For survival the following censoring reasons are possible:

- Alive
- Lost to follow-up

For PFS and TTP (and therefore duration of responses) the following censoring reasons are possible:

- Ongoing without event
- Lost to follow-up
- Withdrew consent
- Adequate assessment no longer available*
- Event documented after two or more missing tumor assessments (optional, see Table 3-2)
- Death due to reason other than underlying cancer (*only used for TTP and duration of response*)
- Initiation of new anti-cancer therapy

*Adequate assessment is defined in [Section 14.1.3.2.7](#). This reason is applicable when adequate evaluations are missing for a specified period prior to data cut-off (or prior to any other censoring reason) corresponding to the unavailability of two or more planned tumor assessments prior to the cut-off date. The following clarifications concerning this reason should also be noted:

- This may be when there has been a definite decision to stop evaluation (e.g. reason="Sponsor decision" on study evaluation completion page), when patients are not followed for progression after treatment completion or when only UNK assessments are available just prior to data cut-off).
- The reason "Adequate assessment no longer available" also prevails in situations when another censoring reason (e.g. withdrawal of consent, loss to follow-up or alternative anti-

cancer therapy) has occurred more than the specified period following the last adequate assessment.

- This reason will also be used to censor in case of no baseline assessment.

Clinical Development & Medical Affairs

SOM230 (Pasireotide) LAR and RAD001 (Everolimus)

CSOM230DIC03 / NCT01563354

Multicenter 3-arm trial to evaluate the efficacy and safety of Pasireotide LAR or Everolimus alone or in combination in patients with well differentiated neuroendocrine carcinoma of the lung and thymus -LUNA Trial

RAP Module 3 – Detailed Statistical Methodology

Author: [REDACTED], [REDACTED] Trial Statistician
[REDACTED], [REDACTED] Trial Statistician
[REDACTED], Novartis [REDACTED]
[REDACTED], Novartis Trial Statistician
[REDACTED], Novartis [REDACTED]

Document type: RAP Documentation

Document status: Final 1.0

Release date: 1st April 2020

Number of pages: 48

Document History – Changes compared to previous version of RAP module 3.

Version	Date	Changes
Amendment 1.0	09-Feb-2016	Section 3.4.1 (Core phase analysis) – clarification is added on safety follow up data inclusion for patients who do not enter extension phase.
Amendment 1.0	09-Feb-2016	[Redacted]
Amendment 1.0	09-Feb-2016	[Redacted]
Amendment 1.0	09-Feb-2016	[Redacted]
Amendment 1.0	09-Feb-2016	Section 10.15 (Vital signs): Clarification is added on the value classification (low/normal/high) for baseline and post-baseline measurements. This classification is needed for the shift table output.
Amendment 1.0	09-Feb-2016	Sections 3.2, 7.4, 7.5 – Clarification added that for tumor response related assessments, confirmation of response is required.
Amendment 1.0	09-Feb-2016	[Redacted]
Amendment 1.0	09-Feb-2016	Section 5.3 – Clarified that partial end dates will be imputed to derive prior/concomitant status.
Amendment 1.0	09-Feb-2016	Section 6.3.3 – Table 5 - Brackets for posterior probability intervals updated for consistency with cumulative distribution function. Specified seed to be used for random draws.
Amendment 1.0	09-Feb-2016	[Redacted]
Amendment 1.0	09-Feb-2016	[Redacted]
Amendment 1.0	09-Feb-2016	Section 10.1 – Changed terminology ‘clinically notable adverse events’ to ‘adverse events of special interest’.
Amendment 2.0	10-Oct-2018	Sections 1 and 9.6.2 – Updated using latest version of protocol.
Amendment 2.0	10-Oct-2018	[Redacted]
Amendment 2.0	10-Oct-2018	Section 3.4.2 – Updated to clarify that PFS endpoint will be analyzed on PP Set as well in extension phase analyses.
Amendment 2.0	10-Oct-2018	Section 3.5 – Updated to indicate that protocol deviations will

Version	Date	Changes
		be re-evaluated and PP Set will be used in extension phase analyses as well.
Amendment 2.0	10-Oct-2018	Section 5.2 – Amended list of outputs which will be repeated based on subset of patients entering extension phase.
Amendment 2.0	10-Oct-2018	Section 7.1 – Updated to clarify that PFS endpoint will be analyzed on PP Set as well in extension phase analyses.
Amendment 2.0	10-Oct-2018	Section 7.3 – Clarification added that endpoint is analyzed up to 12 month only.
Amendment 2.0	10-Oct-2018	Section 7.4 – Updated to indicate that endpoint will be rerun during extension phase analyses based on cumulative data.
Amendment 2.0	10-Oct-2018	Section 7.5 – Clarification added that endpoint is analyzed up to 12 month only.
Amendment 2.0	10-Oct-2018	Section 7.6 – Clarification added that endpoint is analyzed up to 12 month only.
Amendment 2.0	10-Oct-2018	Section 7.7 – Updated to indicate that endpoint will be rerun during extension phase analyses based on cumulative data.
Amendment 2.0	10-Oct-2018	Section 7.8 – Updated to indicate that endpoint will be rerun during extension phase analyses based on cumulative data.
Amendment 2.0	10-Oct-2018	[REDACTED]
Amendment 2.0	10-Oct-2018	Section 10 - Updated general statement on extension phase analyses to clarify that analyses performed after extension phase will include cumulative data.
Amendment 2.0	10-Oct-2018	Section 10.1 – Added description of two new AE summary tables.
Amendment 2.0	10-Oct-2018	Section 10.1 – Updated process of groupings of adverse events of special risk.
Amendment 2.0	10-Oct-2018	Section 11 – Clarification added that DMC analyses were performed during core phase only.
Amendment 3.0	15-Aug-2019	Section 3.4.2 – Removed duration of response analysis from extension phase analysis and added clarification that all analyses and data reporting after extension phase will be reported in the extension phase CSR only.
Amendment 3.0	15-Aug-2019	Section 3.6 – Added note on the subset of patients who entered extension phase and listed the analyses for which this subset will be used.
Amendment 3.0	15-Aug-2019	Section 5.2 – Removed prior therapy analyses from the list of analyses that are repeated for extension phase analysis.
Amendment 3.0	15-Aug-2019	Section 5.4.2 – Removed duration of exposure categories.
Amendment 3.0	15-Aug-2019	Section 5.4.3 – Updated the description of relative dose intensity summary table.
Amendment 3.0	15-Aug-2019	Section 7.4 – Removed statement of repeating duration of response endpoint analysis at the time of extension phase analysis.
Amendment 3.0	15-Aug-2019	[REDACTED]

ECHO	Echocardiogram

ECOG	Eastern Cooperative Oncology Group
EOCS	End of core study
EOEP	End of extension phase
EOT	End of treatment
FAS	Full Analysis Set
FEV1	Forced expiratory volume in 1 second
FPFV	First patient, first visit
FVC	Forced vital capacity
GGT	Gamma-glutamyl transpeptidase
H0	null hypothesis
H1	alternative hypothesis
HbA1c	Hemoglobin A1c subtype (glycated hemoglobin)
HDL	High density lipoprotein
IGF	Insulin-like growth factor
IHC	Immunohistochemistry
ILD	Interstitial Lung Disease
i.m.	Intramuscular
INR	International Normalized Ratio
ITT	Intent-to-Treat
K-M	Kaplan-Meier
LAR	Long-Acting Release
LDL	Low density lipoprotein
LLN	Lower limit normal
LPLV	Last patient, last visit
MedDRA	Medical Dictionary for Regulatory Activities
MRI	Magnetic Resonance Imaging
mTOR	mammalian target of rapamycin
MUGA	Multiple-Gated Acquisition
NA	Not Applicable
NCI	National Cancer Institute
NET	Neuroendocrine Tumor
NEU	Neutrophils

p.o.	per os/by mouth/orally
PD	Progressive Disease
PFR-9	Progression-free at Month 9
PFS	Progression-free survival
PFT	Pulmonary function test
PI3K	Phosphoinositide 3-kinase
PP	Per-Protocol
PR	Partial Response
PTT	Partial prothrombin Time
RAP	Reporting Analysis Plan
RDI	Relative dose intensity
RECIST	Response Evaluation Criteria In Solid Tumors
RNA	Ribonucleic acid
SAE	Serious Adverse Event
SD	Stable disease
SGOT	Serum glutamic oxaloacetic transaminase
SGPT	Serum glutamic pyruvic transaminase SSC
TC	Typical carcinoid
T3	Tri-iodothyronine
T4	Levothyroxine
TEAE	Treatment-emergent adverse event
TSH	Thyroid stimulating hormone
TTP	Time to progression
ULN	Upper Limit Normal
Unsch	Unscheduled visit
UNK	Unknown
WBC	White Blood Cell
WHO	World Health Organization

1 Statistical methods planned in the protocol

This Report Analysis Plan (RAP) contains details of the statistical methods that will be applied for the final analyses to be incorporated into the CSR. This document is based on the clinical trial protocol version no. 5 dated November 7, 2016.

The purpose of this study is to assess the efficacy and safety of pasireotide long-acting release (LAR) and everolimus alone or in combination.

The rationale for this study is based on both preclinical and clinical considerations:

- Combined inhibition of the IGF-1-, the PI3K- and the mTOR-pathways by pasireotide and everolimus may control tumor growth more effectively than either compound alone.
- Combination of everolimus with sandostatin LAR seems to improve progression free survival in NET patients. Thus the combination of everolimus with pasireotide LAR might result in even better tumor control.

This is a prospective, multicenter, randomized, open-label, 3-arm, phase II study with a single-stage design in each arm to evaluate the efficacy and safety of pasireotide LAR and everolimus alone or in combination in the treatment of patients with well differentiated neuroendocrine carcinoma of lung and thymus.

The number of evaluable patients enrolled is targeted to be 120 with 40 patients randomized to each arm as follows:

- Arm 1 treatment with pasireotide LAR (SOM230) (60 mg/month i.m.),
- Arm 2 treatment with everolimus (RAD001) (10 mg/day p.o.), and
- Arm 3 treatment with pasireotide LAR (60 mg/month i.m.) and everolimus (10 mg/day p.o.)

Randomization is stratified by histological grade of well-differentiated tumor (typical carcinoid (TC) vs. atypical carcinoid (AC)) according to the World Health Organization (WHO) classification and line of treatment (1st line vs. others).

The study is designed to assess the activity, safety, and tolerability of the therapy with pasireotide LAR and/or everolimus in each arm separately following a Fleming single-stage design. Each arm is independently evaluated using the decision rules given in the sample size calculation (see Section Determination of sample size).

This study consists of a core study and an extension phase. Patients will receive treatment with study drug(s) for a period of 12 months or until one of the following occur:

- radiologically documented disease progression
- start of new cancer therapy
- intolerable toxicity
- withdrawal of consent

- discontinuation due to any other reason.

Patients will be considered to have completed the core study after the 12 month evaluation has been performed. Patients who are presenting clinical benefit from the treatment with combination or monotherapy with pasireotide LAR and everolimus are permitted to continue treatment after the 12 month treatment period until progression as long as they do not fulfill any of the study discontinuation criteria or as long as the Clinical Trial ceases to be in the interests of the health of the Clinical Trial Patients, or until the pasireotide and/or everolimus development programs is discontinued, whichever comes first.

The end of the study is defined as the last visit two years after treatment start of the last randomized patient or when all patients have progressed whichever comes earlier.

Data will be analyzed by [REDACTED] according to the data analysis section 10 of the study protocol which will be available in Appendix 16.1.1 of the Clinical Study Report (CSR).

2 Discrepancies between RAP and protocol-specified analyses

The following discrepancy exists between the Reporting Analysis Plan (RAP) and the study protocol version 05, dated 7th November 2016. This discrepancy has become apparent during development of the RAP.

[REDACTED]

[REDACTED] At the RAP review stage it was decided that 95% confidence intervals will be displayed instead following template conventions and presentation methods for other parameters.

3 Statistical and analytical plans

3.1 Primary objective

- To evaluate the efficacy of pasireotide LAR and everolimus alone or in combination in progressive patients with a well differentiated neuroendocrine tumor of the lung or thymus. The primary endpoint is defined as the proportion of patients who are progression-free at 9 months, according to response evaluation criteria in solid tumors (RECIST V.1.1).

3.2 Secondary objectives

- To assess overall progression-free survival (PFS) throughout the study in patients with a well differentiated neuroendocrine tumor of the lung or thymus. The endpoint “**progression-free survival (PFS)**” is defined as the time from first study drug administration to objective tumor progression or death from any cause, according to RECIST V. 1.1.
- To assess the **disease control rate** of pasireotide LAR and everolimus alone or in combination, at 12 months, in patients with a well differentiated neuroendocrine tumor

of the lung or thymus. Disease control rate is defined as the proportion of patients showing a best overall response of complete (CR) or partial (PR) response or stable disease (SD) according to RECIST V.1.1

- To assess the time to response, duration of response, objective response rate and best overall response of pasireotide LAR and everolimus alone or in combination during 12 months of treatment in patients with a well differentiated neuroendocrine tumor of the lung or thymus. The endpoint **“time to response”** is defined as the time from start of treatment to the first objective tumor response (PR or CR) observed, according to RECIST V.1.1. The endpoint **“duration of response”** is defined as the time from onset of the first objective tumor response (CR/PR) to objective tumor progression or death from any cause. Tumor response will be analyzed using the criteria of confirmation, i.e. patients will need to have confirmed CR or PR overall assessment before PD or end of core phase measured at least 4 weeks apart each other to be included in the subset of responders. The endpoint **“objective response rate”** is defined as the percentage of patients showing a best overall response of CR or PR according to RECIST V.1.1. criteria. Objective response rate will be summarized at 9 months and again at 12 months. The endpoint of **“best overall response”** is defined as the best response recorded from the start of the treatment until disease progression/recurrence, taking as a reference for PD the smallest measurements recorded since the treatment started.
- To assess the biochemical response rate (BRR), duration of biochemical response (DBR) and biochemical progression-free survival (BPFS) of pasireotide LAR and everolimus alone or in combination in patients with a well differentiated neuroendocrine tumor of the lung or thymus. The endpoint **“biochemical response rate (BRR)”** is the percentage of patients showing normalization, i.e. return to within normal ranges, or a decrease of $\geq 30\%$ from baseline of serum Chromogranin A (CgA) concentrations compared to baseline. The endpoint of **“duration of biochemical response (DBR)”** is defined as the time from the first documentation of biochemical response to the first documentation of biochemical progression (defined as an increase of serum CgA levels $\geq 25\%$ versus baseline) or to death due to any cause, whichever occurs first. The endpoint of **“biochemical progression free survival (BPFS)”** is the time from the first study drug administration to the first documentation of biochemical progression or to death due to any cause, whichever occurs first. Biochemical progression is defined as an increase of serum CgA levels $\geq 25\%$ versus baseline. Additionally, the biochemical response on the basis of urine 5-hydroxyindole acetic acid (5HIAA) will be assessed.
- To assess the safety and tolerability of pasireotide LAR and everolimus alone or in combination as measured by rate and severity of adverse events in patients with a well differentiated neuroendocrine tumor of the lung or thymus. Safety will be assessed using the Common Terminology Criteria for Adverse Events (CTCAE), version 4.0. Incidence of adverse events (AEs), serious adverse events (SAEs), changes from baseline in vital signs, ECG tracings and laboratory results (hematology, blood chemistry) will be reported.

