7.2.1.1.2 Response evaluation by RECIST V. 1.1

The same method of assessment and the same technique should be used throughout the study to characterize each identified and reported lesion at baseline and during follow-up.

Each center must have a designated radiologist or other physician responsible for the interpretation of X-rays, MRI or CT scans and the response evaluation according to RECIST V. 1.1 criteria. The same physician should perform the evaluation for the entire duration of the study. All radiology evaluations will be performed by the local physician.

Scans to allow measurement of all target lesions will be performed routinely every 3 months. If an initial observation of partial or complete response is made, a confirmation scan should be obtained no less than 4 weeks and no more than 6 weeks after the initial observation.

Response evaluation will be performed according to the RECIST V. 1.1 criteria ([Eisenhauer et al. 2009](#)).

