3.4.1 Core phase analysis

For the core analysis, the data cutoff will be the 12 month or end of core phase evaluation and the analysis will take place after the last randomized patient has completed the 12 Month evaluation, or discontinued the study treatment due to progression or start of new anti-cancer therapy.

Only data from the 12 month core phase will be used in the core analyses, any data from the extension phase will be excluded. For patients who do not enter extension phase, safety follow up data (if available) will be included in the core analyses.

All events with start date before or on the 12 month evaluation date and with an end date after the 12 month end date will be reported as '*continuing at the end of the core phase*'. The same rule will be applied to events starting before or on the 12 month evaluation date and not having documented end date. This approach applies, in particular, to adverse event and concomitant medication reports. For these events, the 12 month evaluation date will not be imputed and therefore will not appear in the listings.

Imputation of end date will be performed with the 9 or 12 month evaluation date when needed for specific analyses e.g. exposure and dose intensity computation.

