7.5 Objective Response Rate

The objective response rate is defined as the proportion of patients showing a best overall response of CR or PR during the core study (i.e. up to 12 months) according to RECIST V. 1.1 criteria. For the assessment of SD as best overall response, there is no specific time needed from baseline as the first tumor evaluation takes place after 12 weeks (at Visit 8) from randomization thus conforming the required minimum time of 6 weeks from randomization based on RECIST 1.1 guidelines. Therefore, the best overall response is interpreted as the best response recorded from the start of the treatment until disease progression/recurrence, death from any cause or until the patient withdraws consent, whichever is earliest. In order to have a best overall response of CR or PR, response must be confirmed by another response assessed at least 4 weeks after the initial response. The objective response rate will be calculated at 12 months and displayed with 95 percent exact binomial confidence intervals (implemented using SAS procedure FREQ with EXACT statement for one-way tables) [Clopper & Pearson, 1934]. Frequencies of each response will also be included. This will be carried out for all patients in the full analysis set.

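### The SAP's core-phase confirmation rule means that a CR or PR first seen at Week 52 can never count, leaves no slack at Week 48, and SAP 7.5 omits the 9-month ORR

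*SAP*

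**What the plan says.** SAP 3.2 defines who is a responder: "patients will need to have confirmed CR or PR overall assessment before PD or end of core phase measured at least 4 weeks apart". SAP 7.5 limits ORR to a "best overall response of CR or PR during the core study (i.e. up to 12 months" and adds that "response must be confirmed by another response assessed at least 4 weeks after the initial response".

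SAP 3.4.1 sets the cut: "the data cutoff will be the 12 month or end of core phase evaluation", and "Only data from the 12 month core phase will be used in the core analyses, any data from the extension phase will be excluded". SAP 3.4.2 repeats only PFS and safety after the extension. Sections 7.7 and 7.8 add the two biochemical time-to-event endpoints. ORR, time to response and duration of response are not rerun.

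Protocol 7.2.1.1.2 asks sites for something that can run past this cut: "a confirmation scan should be obtained no less than 4 weeks and no more than 6 weeks after the initial observation". Protocol Appendix 1 (14.1.3.1) requires confirmation before progression and sets no end-of-core limit on the confirming scan.

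On timing of the rate itself, SAP 3.2 says "Objective response rate will be summarized at 9 months and again at 12 months", in line with Protocol 3.2 and 10.5.2. SAP 7.5 says only "The objective response rate will be calculated at 12 months".

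**The concern.** The endpoint is response during 12 months of treatment, and the Week 52 scan lies inside that period. A patient whose tumour first meets PR criteria there has responded within the period but is classed as SD, because the confirming scan falls on the wrong side of a data cut. In time to response (SAP 7.3), such a patient, if progression-free, is censored at the last adequate assessment, which is the date of the response itself. The patient also drops out of the responder set for duration of response (SAP 7.4).

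Sections 7.3 and 7.4 place the first response in the core phase and require confirmation, but do not say that confirmation must also fall in core. Section 3.2 does. Programmers working from different sections could derive different responder sets.

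The 9-month ORR is at the primary time point. It is promised in SAP 3.2 but has no method in SAP 7.5.

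**Working it through.** **Inputs.** SAP Table 2 gives planned scan days as 7k + 1 for week k, with a Week 48 slot of Days 295 to 351 and a Week 52 slot of Days 352 to 379. The minimum confirmation gap is 4 weeks, or 28 days (SAP 3.2, 7.5). The protocol's confirmation interval is 4 to 6 weeks. A ±7-day tolerance for monthly visits appears in Protocol 7.2.2, for safety assessments only. Arms have 41, 42 and 41 patients (Protocol, Amendment 5 rationale).

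**The plan's scan days reproduce.** Week 48: 7 × 48 + 1 = 337. Week 52: 7 × 52 + 1 = 365. Planned gap: 365 − 337 = 28 days.

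**First response at Week 52.**
- Earliest qualifying confirmation: 365 + 28 = Day 393. The protocol's interval ends at 365 + 42 = Day 407 (Weeks 56 to 58).
- The end-of-core evaluation is itself the cut-off, so nothing after it counts. Day 393 falls in the Week 64 slot (Days 380 to 491).
- Two scans inside the Week 52 slot are at most 379 − 352 = 27 days apart, one short of the minimum.
- The share that can be confirmed is therefore 0.

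**First response at Week 48.** The protocol's confirmation interval is 337 + 28 = Day 365 to 337 + 42 = Day 379, which the SAP's Week 52 slot covers entirely. A gap of exactly 28 days meets the rule. Any loss comes from drift. With shifts a (Week 48) and b (Week 52) in whole days, the gap is 28 + b − a, and confirmation fails when b < a.

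| Assumption on scan dates | Share with gap under 28 days |
|---|---|
| Both on schedule | 0% |
| Site applies the protocol's 4-week minimum when booking | 0% |
| Week 48 ±7, end-of-core scan 0 to +7 | 28/120 = 23.3% |
| Each uniform over its SAP slot | 378/1596 = 23.7% |
| Independent uniform ±2 | 10/25 = 40% |
| Independent uniform ±7 | 105/225 = 46.7% |

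The second row is feasible: a Week 48 scan as late as Day 344 needs Day 344 + 28 = 372, which is Day 365 + 7 and inside the Week 52 slot.

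**Effect per patient.** 1/41 = 2.4 percentage points of ORR (also 2.4 at n=42).

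**Scale, for illustration only.** The protocol cites a phase II pancreatic NET study with partial-response rates of 4.4% and 9.6%. Applied to 41 patients these give 1.8 and 3.9, or about 2 to 4 responders per arm, so one lost response would be a quarter to a half of the estimate. The protocol also cites 2.0% CR+PR for pasireotide LAR in a phase III carcinoid study, which is under one responder per arm.

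**The case against.** The strongest defence is that this is a choice of endpoint. Requiring confirmation within the same 12 months is conservative, was specified in advance, and is the same in every arm. Any fixed cut-off loses responses at the last scan, and ORR is descriptive with no test attached. It follows that the rule cannot be called biased in an absolute sense. It is stricter than the protocol, which asks for the later scan and requires confirmation only before progression.

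A second defence is that few patients can be affected. A first response at Week 52 must appear in the four weeks after Week 48, only 43 of 124 patients completed core, and several cited response rates are low. That stands; the number may be zero.

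A reader might infer that about half of Week 48 responses are lost. The documents do not support this. The ±7 days is not stated for tumour scans, independent drift is an assumption, and a site that follows the protocol's 4-week minimum loses none.

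A reader might also assume that the missing confirmation scan always exists. Protocol 7.2.1.1.1 recommends extension scans every 3 months, but Table 7-2 leaves their frequency to the investigator.

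Finally, the core analysis was run on 26 February 2016, so changing the responder definition now would follow known results. That bears on how a revised result is labelled.

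**Conclusion.** The point holds for Week 52. Under SAP 3.2, 3.4.1 and 7.5 read together, no response first seen at the last core scan can count, and no later analysis repairs this. The conclusion needs no assumption beyond the stated schedule.

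For Week 48 the finding is only that the design has no slack: 0% loss on schedule, and up to about 47% under independent ±7-day drift, which is the top of an assumed range. A strict reading of SAP 3.2 could even exclude the Week 52 scan as a confirming scan. The cut-off wording in SAP 3.4.1 points against that, but the SAP should say so.

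The number of patients affected cannot be computed from the documents and is probably small, at 2.4 percentage points each. DCR is untouched because an unconfirmed CR or PR still counts as SD; PFS and the Month 9 primary endpoint do not use confirmation of response.

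The 9-month ORR is a separate and plain inconsistency. A reader might conclude that it was never produced. The output shells are not in the documents, so they show only that SAP 7.5 gives no method for it.

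**What to change.** In SAP 3.2, 3.4.1, 7.3, 7.4 and 7.5, use one rule: a CR or PR first observed on or before the end-of-core visit is confirmed if the next adequate scan at least 4 weeks later, including a confirmation scan or the first extension scan, shows CR or PR before PD. Keep the first-observation date as the response date, so the endpoint stays within 12 months. State that the Week 52 scan may confirm a Week 48 response.

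In SAP 7.5, add ORR at 9 months: responses first observed by the Week 36 window (to Day 294), with the same confirmation rule.

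Because the core analysis has been run, report the re-derived ORR, time to response and duration of response as supplementary in the extension CSR, beside the core-only results.

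The cost is SAP wording, programming and the use of one post-core scan per late responder. With extension scan timing partly at the investigator's discretion, the interval to confirmation will vary, and patients without such a scan remain unconfirmed. Of the 43 core completers, 41 entered the extension, so few should lack the opportunity.
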